1.3 SCHEDULE OF ACTIVITIES (SOA)

All activities listed will be administered on both sites.

	Screening Day -7 to -1	Baseline Day 0	Study Visit 2 Day 56 +/- 14 day	Study Visit 3 Day 84 +/- 14 day	Final Study Visit 4 Day 112 +/- 14 day
Procedures					
Informed consent	X				
SCID-5	X				
WRAT-4	X				
Demographics		X			
Medical history		X			
BACS		X			
VRFCAT		X			
MINI		X			
PSQI		X			
WHODAS 2.0		X			
PHQ-9		x			
PANSS		X	X	X	X
Calgary Depression Scale (CDSS)		X	X	X	X
Treatment Rationale Scale		X	X	X	X
CSSR-S		X	X	X	X
IA on METER and VLMT		X	X	X	X
Metacognitive WCST		X	X	X	X
Informant-Rated SLOF		X			X
GPS			X	X	X
Compensatory Cognitive Strategies Scale (Informant)		X			X
CAINS Motivation		X	X	X	X
Defeatist Performance Beliefs		X	X	X	X
Client Satisfaction Questionnaire (CSQ)		X	X	X	X
Negative Effects			X	X	X
Trials and Coaching Sessions Completed			X	X	X
HVLT			X	X	X
Metacog ER-40			X	X	X
Brief Regulation of Motivation Scale			X	X	X
Karolinska Sleepiness Scale			X	X	X
GAD-7			X	X	X

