3 OBJECTIVES AND ENDPOINTS

In this pilot project, there are two objectives. Firstly, we will evaluate, in an open trial, whether iTEST is acceptable, indexed by adherence, and engages IA as a target, indexed by improved IA on trained

tasks and transfer on an untrained task in a different domain. Secondly, we will evaluate optimal dosing of the intervention, by whether go/no-go criterion for improvement is achieved at 8, 12, or 16 weeks.

Our go/no go criteria are threefold: 1) To demonstrate feasibility, the average adherence must be equal to or exceed 75%, 2) To show target engagement, we require a significant improvement in IA ($d > .50$) on both trained tasks, and 3) To show transfer of training, we require significant improvement in IA ($d > .50$) on the untrained Wisconsin Card Sorting Task. Criteria may be met prior to 16 weeks, at weeks 8 or 12 (Note: all participants continue through 16 weeks).

OBJECTIVES	ENDPOINTS	JUSTIFICATION FOR ENDPOINTS
Primary		
To evaluate the acceptability and preliminary impact on our target, IA	
Adherence defined as the ratio of completed mobile prompts completed divided by the number possible – 75% is the criterion
 
Clinically significant (Cohen's $d > 0.5$) improvement in trained introspective accuracy as measured by IA on our Verbal Learning and Memory Test and Mobile Electronic Test of Emotion Recognition tasks. These are administered 6x per week for 16 weeks.
 
Clinically significant (Cohen's $d > 0.5$) improvement in untrained introspective accuracy (global resolution score) on the WCST. The WCST is administered at baseline, 8, 12 and 16 weeks.
	
Adherence at a level of 75% is generally accepted in mobile intervention studies such as this
 
The reason that trained tasks are part of our Go/No Go criteria is because lack of improvement on trained tasks would call into question the ability of iTEST to modify IA, and would indicate need for program revisions. IA is calculated as the discrepancy (absolute) between each trial's correct performance from that estimated by the participant, which is nested within sessions and weeks.
 
An additional Go/No Go component is transfer of training to an untrained task-based measure of IA, the Meta-Cognitive Wisconsin Card Sorting Test¹³. IA on this task is also associated with functioning and improvement on this task would support that iTEST

OBJECTIVES	ENDPOINTS	JUSTIFICATION FOR ENDPOINTS
		leads to generalized improvement in IA.
Secondary		

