Training involves prompts 6x per week to engage in the Task-Based training, which lasts 10-15 minutes per session and consists of three blocks each of IA on verbal memory and emotion recognition. The reason to deliver task-based training 6x per week was to provide one day off (which can be selected by the participant). Alarms can be silenced for 30-minute intervals (e.g., driving, appointments). If a participant misses a session, they will receive 2 reminders that day to complete it. If they miss two consecutive days (or one day during the first week), participants will be contacted by their Coach to engage in problem solving and motivational support. Our previous data on remote adherence suggested that early adherence was highly predictive of total adherence ($r=.80$)³², so daily first week outreach will occur in case of non-adherence.

Our web-based smartphone compatible software is built around our previously validated VLMT and METER tasks. This flows from a) introductory/instruction screens, b) presentation of stimuli, c) performance assessment (initially with feedback on correctness), and d) IA queries (how many words/faces correct, confidence) e) feedback about IA. Items b-e are then repeated for the second and third trials of the tasks. Stimuli include variable numbers of words or faces with the number of stimuli randomly ordered per session and derive from a large normed corpus so that stimuli are not repeated. Training is graduated in four steps: (1) The first skill is correctly identifying the number of stimuli presented (task awareness); (2) After 3 consecutive sessions in which the number of stimuli is correctly identified, participants are provided *trial-by-trial* feedback on correctness of response and scoring is based on correct assimilation of trial-by-trial feedback to global estimation of performance (e.g., “you indicated that you got 10 correct; however, you actually got 8 correct”); (3) after 3 consecutive sessions/days of high IA (+/- 1 discrepancy between actual correct and self-assessed), training then progresses to presentation of stimuli without trial-by-trial feedback wherein more global estimates are

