- 9). The smartphone is used by the participant's fingers and will not enter the participant's body nor does it involve a break in skin, have contact with the mucous membrane or internal body cavity

Additional Screenshots of the software are attached to this protocol.

Transportation: For participants who are unable to meet in our research office space due to physical disability or financial reasons, we will use the UCSD Lyft Concierge service for transportation, provided that residence is within a 25-mile radius of UCSD. Participants will **NOT** be required to pay for the Lyft rides as the research study will cover the costs of these rides.

To use Lyft participants will be providing name, pick-up location, drop-off location, and phone number to the research staff, which will then be used by the Lyft driver. This information will only be given to the Lyft drivers after consent over the phone (during the phone screening procedures) and by providing written consent in the Informed Consent document. Participants phone number and the driver's phone number will be masked during the active ride through a third party system. Neither participant nor the driver will have access to each other's real phone numbers. Personal health information (PHI) will not be shared with Lyft.

If participants choose to their own mode of transportation, they are subject to any associated to charges or fees, however, they will not be required to pay for parking at our research office for the duration of the visit.

Compensation for assessments and screening:

Participants are paid up to \$220.00 for in-lab assessments. A total of \$20 is provided for completing the screening portion of Visit 1 and participants are compensated \$50 for completing the rest of that visit. For Visit 2, 3, and 4 participants are compensated \$50 for each.

We also have assessments delivered through the mobile device at Baseline (Visit 1) and each of the weeks that coincide with lab visits (i.e., weeks 9, 13, and 17).. Assessments will involve 6 days of completing brief mobile assessments that closely mirror the iTEST training, and participants will be paid 5 dollars for each of the 6 mobile assessments that they complete. The number of days completed is factored to the compensation and so participants can receive up to 30 dollars for completing all 6 assessments. Thus, over four assessment days, participants can be compensated up to 120 dollars (30 x 4 assessments).

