9.2 SAMPLE SIZE DETERMINATION

We used the Monte Carlo simulation capabilities of Mplus version 8.4⁵² to perform our power analyses. To determine our levels of power to detect changes in IA for the list-learning task or emotion recognition tasks equivalent to $d = |0.50|$ for R61 Aim 1, we specified three-level models with 1000 replications each wherein trials ($t = 18$) were nested within weeks ($w = 8, 12, \text{ or } 16$) that were further nested within persons ($n = 60$ or 48 in the case of 20% attrition). These models were similar to Figure 1 with the exception that changes in IB and IA at Level 3 were not regressed on intervention condition. As can be seen in Table 1, our power levels were excellent (i.e., $> .90$) across all combinations of sample size and week size, ranging from .91 for detecting changes in IA of $d = -0.50$ at 8 weeks with 48 participants to .97 for detecting changes in IA of $d = 0.50$ at 16 weeks with 60 participants.

To determine our levels of power to detect transfer-of-training for R61 Aim 1 and optimal dosing for Aim 2, we again specified three-level models with 1000 replications each wherein trials ($t = 18$) were nested within weeks ($w = 8, 12, \text{ or } 16$) that were further nested within persons ($n = 60$ or 48 in the case of 20% attrition). However, we modified these models such that they included an additional Truth and Bias model for the WCST transfer of training target at Level 2 that had a change in IB of $d = -0.50$ across the weeks. To reflect the fact that this in-laboratory tasks would only be measured at 0, 4, 8, 12, and 16 weeks, we specified that these measurements should have 62.5% missing data in the simulations (e.g., only completing 3 out of 8 weeks). As can be seen in Table 2, we should have more-or-less adequate levels of power to detect a change in IB for the in-lab assessment at 16 weeks with 48 participants (power = .77) and adequate power to detect a change in IB for the in-lab assessment at 12 and 16 weeks with 60 participants (power = .78 and .83, respectively).

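### The plan conflicts on where the trained-IA go statistic comes from, and under the weekly training-data model change in IA is confounded with training stage

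*Combined protocol and SAP*

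**What the plan says.** Two sets of statements describe the trained-IA endpoint.

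**Weekly training data.** The endpoint table in Section 3 says of the VLMT and METER: "These are administered 6x per week for 16 weeks". It defines the score thus: "IA is calculated as the discrepancy (absolute) between each trial's correct performance from that estimated by the participant". Section 6.1.1 says each training session "consists of three blocks each of IA on verbal memory and emotion recognition". In the power model of Section 9.2, "trials ($t = 18$) were nested within weeks", with 8, 12 or 16 weeks. Section 9.4.1 regresses each week's IA on week number.

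**Separate assessments.** The Schedule of Activities (Section 1.3) has a row "IA on METER and VLMT" marked only at baseline and Visits 2, 3 and 4. The compensation text in Section 6.1.1 places mobile assessments at baseline and weeks 9, 13 and 17: "Assessments will involve 6 days of completing brief mobile assessments that closely mirror the iTEST training". Section 9.1 states the hypothesis as a pre-post change divided by the baseline standard deviation.

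**Training stages.** Section 6.1.1 puts "performance assessment (initially with feedback on correctness") ahead of the IA query and describes four stages:

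1. Identify the number of stimuli.
2. Estimate the number correct with trial-by-trial correctness feedback.
3. After three consecutive sessions within +/-1, "training then progresses to presentation of stimuli without trial-by-trial feedback wherein more global estimates are" trained.
4. Add certainty ratings that feed into the score.

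**The concern.** In stage 2 the participant learns whether each response was right before estimating how many were right. A small discrepancy there can reflect counting the feedback rather than introspection. Stage 3 removes that aid, and stage 4 changes the response format and the scoring incentive. If the go statistic is built from training sessions, the measuring conditions change within each person over time, and the timing depends on the outcome being measured. Section 4.1 describes a single-arm trial, so no comparison group removes the artefact, and Section 9.4.1 has no term for stage.

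Two of the three IA go criteria (VLMT and METER) rest on this measure, as does the choice among 8, 12 and 16 weeks. Those decisions determine whether the R33 trial proceeds and for what duration.

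**Working it through.** **1. Which data the power model uses.** Six sessions per week (Section 3) times three blocks per task per session (Section 6.1.1) gives 6 x 3 = 18, matching t = 18 in Section 9.2. This alone does not separate the sources, since a 6-day assessment burst with three trials per task per day also gives 18. The number of weeks does: bursts occur in only four weeks, so 8, 12 or 16 consecutive weeks can only be training weeks. Trials per task:

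| Source | First evaluation | Second | Third |
|---|---|---|---|
| Weekly model | 18 x 8 = 144 | 18 x 12 = 216 | 18 x 16 = 288 |
| Bursts, including baseline | 18 x 2 = 36 | 18 x 3 = 54 | 18 x 4 = 72 |

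**2. The plan's power figures.** Section 9.2 gives .91 (n = 48, 8 weeks) and .97 (n = 60, 16 weeks). A paired t-test against zero with standardised mean change 0.5 and two-sided alpha 0.05 (assumed; the plan states none) has noncentrality 0.5 x sqrt(n), or 3.46 and 3.87, and power .924 and .968. These are close to the stated values. This is an approximation, because the variance inputs to the three-level simulation are not given.

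**3. When feedback is present.** Stage 1 needs at least three sessions and stage 2 at least three more, so the earliest feedback-free training session is session 7, the first of week 2. All week 1 training data therefore come from stages 1 and 2. Training starts the day after the initial session, so training data contain no pre-training baseline.

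**4. Size of the artefact (illustration, all inputs assumed).** Suppose true introspection does not change, mean absolute error is 2.0-2.4 items without feedback and 0.8-1.2 with it, and the baseline SD is 0.8-1.2. Against a feedback-free baseline, apparent d = share in feedback stage x (error without - error with) / SD.

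- 30% in the feedback stage: lowest 0.3 x (2.0 - 1.2)/1.2 = 0.20; highest 0.3 x (2.4 - 0.8)/0.8 = 0.60.
- 50%: lowest 0.5 x 0.8/1.2 = 0.33; highest 0.5 x 1.6/0.8 = 1.0.

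The sign reverses if early weeks are feedback-heavy. Let delta be the effect of feedback in baseline SDs. If everyone starts with feedback and half later work without it, apparent d = -0.5 x delta, or -0.25 to -1.0 for delta of 0.5 to 2.

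**5. The share in the feedback stage is not known.** Assume independent sessions, the fastest possible stage 1, and a fixed chance p per session of meeting the +/-1 rule. Simulation then leaves 76% in stage 2 at week 8 for p = 0.2, 42% for p = 0.3 and 3% for p = 0.5; at week 16 the shares are 55%, 16% and 0%. The plan does not say whether +/-1 applies to every trial or to a session average, so p cannot be pinned down.

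**The case against.** The strongest reply is that the endpoint may never have been meant to come from training sessions. The Schedule of Activities row, the paid assessment weeks and the baseline-SD hypothesis all fit a burst-to-burst contrast, and the Section 3 sentence can be read as describing how often the tasks are given. This stands as evidence of conflict. A reader might infer that the trained-IA endpoint is definitely contaminated; the documents do not support that, because they never settle the source. Nor do they remove the problem: the feedback condition in the bursts is not stated, and the only model written down uses every week.

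A reader might also infer that the artefact could carry the trial to a go. It could not do so alone. Section 3 also requires d above .50 on the untrained WCST, which has no training stages.

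A third reply is that participants who simply count feedback will tend to satisfy the +/-1 rule and leave stage 2, so a large share held there is not a given. That is fair, and so the 30% and 50% shares are assumptions rather than estimates.

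Finally, the illustration uses absolute error (Section 3), whereas Section 9.4.1 models IA as the slope of judgement on performance. Feedback should also push that slope toward accuracy, but nothing here quantifies it.

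**Conclusion.** The documents contradict each other on the source of the trained-IA go statistic: Sections 3, 9.2 and 9.4.1 against Section 1.3, the assessment text in 6.1.1, and 9.1. If the weekly model is followed as written, change in trained IA is confounded with training stage, with neither a stage term nor a control arm to separate them.

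The bias has no fixed direction. It can raise d on both trained tasks, or hide a real gain when feedback is withdrawn and lead to a false no-go or a later selected week. The illustrative ranges in the working show that 0.5 is reachable without true change, not that it would be reached. They depend on the assumed errors, SD and shares. This should be resolved before the go/no-go analysis, because the planned model can return a wrong d.

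**What to change.** - In Sections 3, 9.2 and 9.4.1, name the change from the baseline mobile burst to the week 9, 13 and 17 bursts as the trained-IA go statistic, and align this with Sections 1.3 and 9.1.
- Run every burst in one fixed format for all participants: the same list-length mix, no correctness or IA feedback before or between estimates, and no certainty-linked scoring.
- Report training-session IA descriptively, by stage.
- Rerun the three-level simulation for four occasions of 18 trials per task.

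**Cost.** The bursts are already scheduled and paid for, so the change is plan wording plus a fixed configuration of the task software; whether the software allows this needs confirming. The statistical price is fewer occasions than the weekly model. As a guide, take a paired contrast against zero at d = 0.5 on the baseline SD, equal SDs and two-sided 0.05, so that the standardised mean change is 0.5/sqrt(2(1 - r)). With pre-post correlation r = 0.5 this is 0.50, with power about .92 (n = 48) and .97 (n = 60). With r = 0.3 it is 0.42, with power about .82 and .90. The correlation is not given in the plan, and these figures do not replace the new simulation.

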4 STUDY DESIGN

Leave blank. Text should be included under the relevant subheadings below.

4.1 OVERALL DESIGN

Hypothesis:

Target Engagement Hypothesis: Participants' adherence and average changes in IA for the mobile tasks and pre- post differences in meta-cognitive WCST will meet or exceed our go/no go criteria

Optimal Dosing: Target engagement may occur prior to 16 weeks, at week 8 or 12. We would select the optimal dose for the R33 is determined by selecting the earliest assessment point that reaches go/no go criteria - all participants receive the same dose

Phase of the trial, if applicable: This is a pilot behavioral intervention and so study phases are somewhat difficult to apply but would be mostly consistent with a Phase Ib study that is investigating acceptability and a preliminary effect in a diseased population

Design of Trial: Single arm, unblinded, open pilot trial.

Methods used to minimize bias: Measures are standardized and accepted endpoints and the sample has few exclusion criteria for entry

Dosing: All participants receive the same dose. We will investigate the point at which (among 8, 12, and 16 weeks) go/go criteria are met.

Intervention groups: This is a single arm trial and the duration of the intervention is 16 weeks.

Sites: There will be 2 sites – UCSD is the prime site and University of Texas at Dallas will be the secondary site with their own IRB.

Study Intervention: iTEST

Interim Analysis: No interim analysis is planned

Stratification: None

Name of sub-studies, if any, included in this protocol: None

4.2 SCIENTIFIC RATIONALE FOR STUDY DESIGN

The rationale for the study design is to provide a test of acceptability and target engagement. The design was chosen according to the sponsor's (NIMH) experimental therapeutics framework, which supports testing of novel therapeutics with a sequence of trials first evaluating target engagement and then, if go/no go criteria are met, an efficacy trial of the intervention wherein outcomes are evaluated and the relationship between target engagement and outcomes is evaluated. This protocol is aimed at evaluating target engagement and so an open trial was selected. Since there are no prior studies evaluating whether introspective accuracy is modifiable in schizophrenia, we have selected an open pilot trial format.

4.3 JUSTIFICATION FOR DOSE

Our rationale for the dosing framework is as follows. Our starting dose is that in-lab IA intervention in healthy adults occurred over 8 weeks and included 2160 total trials and 80 instances of IA feedback (in aggregate ~6 hours)¹⁴. iTEST at 8 weeks equates to 4320 trials and 188 rounds of feedback (8-10 hours), which is about twice the dose of the in-person IA intervention in healthy adults¹⁴. The reason to start with a more intensive “dose” of iTEST in psychotic disorders is that we would expect a higher level of impairment in IA than in a healthy population. We will then extend this period to 16 weeks with additional evaluations at 12 and 16 weeks, yielding a maximum of 16-20 hours of training in aggregate. . This *maximum* dose of training at 16 weeks is 75% of the mean training duration reported in a 2020 meta-analysis of available computerized cognitive training¹⁹ and ~50% of the average duration of cognitive remediation programs²⁰. When considering the amount of epochs of training, the dose is lower than the number of interactions required in our prior ecological momentary interventions²¹⁻²³.

4.4 END OF STUDY DEFINITION

A participant is considered to have completed the study if he or she has completed all phases of the study including the last visit or the last scheduled procedure shown in the Schedule of Activities (SoA), Section 1.3.

The end of the study is defined as completion of the last visit or procedure shown in the SoA in the trial globally.

5 STUDY POPULATION

Leave blank. Text should be included under the relevant subheadings below.

5.1 INCLUSION CRITERIA

There are two populations in this study. The iTEST study population consists of people who are adult outpatients with diagnoses of schizophrenia (n=60, divided equally between UCSD and U Texas at Dallas). There are also informants nominated by the participant who provide ratings on the two scales (one pertaining to functioning and the other to cognitive strategies). We detail iTest participants first

Potentially eligible participants recruited through flyers, word of mouth or community presentations will complete a brief screening to review eligibility. That brief pre-screening details the study and consists of questions about basic eligibility. Thereafter an appointment is made for a lab visit provide that basic eligibility questions are met, and the participant is interested in the study.

During recruitment, all participants will receive an initial phone or in-person screening. The phone screening can involve a short survey via REDcap and a 1-on-1 screening call with a researcher. At this point, they will be asked basic demographic information and asked if they have a current psychiatric diagnosis. Only participants who are able to consent for themselves and fully understand the study procedures will be allowed to participate. For remote screening and consenting visits, consents will be obtained via a HIPAA compliant platform such as REDCap.

The screening and trial have the same informed consent.

The Screening which is held in person consists of:

- A questionnaire concerning basic eligibility (e.g., current treatment stability)
- A diagnostic assessment to confirm diagnosis (SCID)
- A measure of reading level (WRAT-4)
- A measure of psychiatric symptom severity (PANSS)

Participants are compensated for completing the screening at a rate of 20 dollars. The duration of the screening is estimated to take 30-40 minutes.

In order to be eligible to participate in this study, an individual must meet all of the following criteria

Inclusion Criteria:

- (1) Voluntary informed consent to participate and capacity to consent as measured by the UCSD Brief Assessment of Capacity to Consent (UBACC)²⁴;
- (2) Age 18 to 65;
- (3) DSM-5 diagnosis of schizophrenia or schizoaffective disorder based on a SCID-5 interview and available medical record review;
- (4) $\geq 6^{\text{th}}$ grade reading level on the Wide Range Achievement Test-4 Reading (WRAT-4) subtest (needed to read instructions on device)²⁵;
- (5) Stable co-treatments (no hospitalizations or medication class changes in 2 months before enrollment). We will determine symptom and medication stability by best-estimate history with information from medical records;
- (6) Availability of a clinician (staff member, case manager, other mental health clinician) or close associate (family member, friend) with at least monthly contact who can be their informant – the purpose of informants is to complete the SLOF which is a rating scale measure of functional ability and the Cognitive Strategies which assess use of compensatory strategies in daily life;
- (7) Minimum level of functional impairment based on milestones, excluding participants who are full-time employed and financially responsible for their household.

Informants are nominated by the participant. As such, we are seeking a partial waiver of consent to reach out them to invite them to participate in the research. Following a standard phone script (see script), informants are invited to participate in the study and their nature of participation is detailed. If verbal consent is obtained, the questionnaires are administered by telephone at the same time as consent.

Our justification for a partial waiver of consent for informants is as follows: 1) The research component involves no more than minimal risk to subjects; 2) The research could not be carried out practicably without the waiver since the informant must be nominated by the participant; 3) The waiver will not adversely affect the rights and welfare of the subjects; and 4) Where appropriate, the subjects will be provided with additional information about their participation.

If a participant's nominated informant cannot be reached or declines participation, we will ask the participant to provide another informant. In the unlikely event that no informants agree to participate, the participant will not be dropped from the study.

